6.6.2 Dose Modification and Management of Liver Toxicity

Elevation of liver enzymes could be a very common finding during the course of regorafenib and pembrolizumab combination therapy. In the ongoing 19497 study of regorafenib and pembrolizumab in HCC patients in first line, as of 06 JAN 2020, 31% of the patients experienced Grade 3 treatment-emergent AE (TEAE) of AST or ALT increase and 6% of them experienced Grade 4 occurrences.

A careful assessment should be done to define the proper etiology of any hepatic alteration found in the course of the study in order to exclude the underlying disease and an immune-mediated hepatic events as possible causes, before defining a liver toxicity as related to the study interventions.

Participants with a history of HBV or HCV with elevated transaminases who meet the criteria below should be evaluated for viral exacerbation/reactivation and viral load and hepatitis serologies (as needed) should be performed for evaluation of viral exacerbation/reactivation:

- Among participants with baseline AST/ALT ≤2×ULN: AST/ALT >5×ULN
- Among participants with baseline AST/ALT >2×ULN: AST/ALT >3×the baseline level
- AST/ALT >500 U/L regardless of baseline level

Page 65 of 141

Table 6–5: Dose Modification Guidance; Specific Guidance for Liver Toxicity

Event	Regorafenib	Pembrolizumab
General instructions:		
If any of below outlined events will occur	r: Monitor liver function tests weekly or more frequently until re	ecovery to baseline or stabilization
• The recommendations regarding dose adjustments and treatment interruptions can be used as support for the clinical decision. A careful decision will be		
made by investigators based on all clinic	cal information, e.g. relatedness to study medications	
 Follow the guidance provided in Table 6 	-6 with respect to Hepatitis B flare, Hepatitis C recurrence or	flare and immune-related hepatitis
 For any G3/4 increases in ALT/AST or b 	oilirubin:	
 If the increases are primarily seen under ongoing regorafenib treatment (e.g. last pembrolizumab infusion was given one week before): Closely monitor for potential de-challenge, i.e. whether a decrease in ALT/AST and/or bilirubin values is seen within 3 days of regorafenib interruption 		
	s seen and/or a further deterioration in liver function is seen: A	dminister corticosteroids (initial dose of 1-2 mg/kg
prednisone or equivalent) for		
	: Directly follow guidance provided in Table 6–6.	

Gastrointestinal bleeding suggestive of portal hypertension (e.g., esophageal or gastric varices)	Discontinue and assess according to guidance given in Table 6–6	Hold and assess + decide on potential restart according to guidance given in Table 6–6
Recurrence of a severe or life-threatening event, or of any of the laboratory abnormalities listed above	Discontinue and assess according to guidance given in Table 6–6	Discontinue and assess according to guidance given in Table 6–6
If the participant is off study treatment therapy for infection, obstruction, or drug/alcohol-related toxicity for more than 3 weeks, or if they have esophageal bleeding, or become CP C at any point	Discontinue and assess according to guidance given in Table 6–6	Discontinue and assess according to guidance given in Table 6–6

 $ALT = alanine\ aminotransferase;\ AST = aspartate\ aminotransferase;\ G1/2/3/4 = Grade\ 1/2/3/4;\ QD = every\ day;\ ULN = upper\ limit\ of\ normal$

a: If reductions are required resulting in a dose of less than 60 mg QD of regorafenib, then regorafenib will be permanently discontinued. For Grade 3 neutropenia, the participant could stay on regorafenib for the first appearance, or hold until resolved to Grade 2 or less, restart at the same dose level or lower after discussion between the investigator and the sponsor.

b: Hold until recovery to Grade ≤ 1 and restart at the same dose level or reduce 1 dose level a (at the investigator's discretion) if hepatic encephalopathy is manageable and reversible, after discussion with the sponsor.

Page 67 of 141

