6.6.2.1 Hepatic Events of Clinical Interest

The following events and laboratory abnormalities, if not associated with disease progression under study per investigator's judgement, are considered as hepatic events of clinical interest (HECI) and must be reported as SAEs (within 24 hours of the investigator's awareness):

- ALT:
 - ALT \geq 5 × ULN if baseline ALT <2 x ULN
 - ALT >3 × baseline level if baseline ALT \geq 2 x ULN
 - Any ALT >500U/L
- Any t-bilirubin >3.0 mg/dL
- Regardless of laboratory values, hepatic decompensation diagnosed clinically, including:
 - New onset of clinically detectable ascites requiring intervention for >3 days
 - Hepatic encephalopathy

Note: These criteria are based upon available regulatory guidance documents. The purpose of the criteria is to specify a threshold of abnormal hepatic tests that may require an additional evaluation for an underlying etiology. The trial site guidance for assessment and follow up of these criteria can be made available. It may also be appropriate to conduct an additional evaluation for an underlying etiology in the setting of abnormalities of liver blood tests including ALT and bilirubin that do not meet the criteria noted above. In these cases, the decision to proceed with additional evaluation will be made through consultation between the study investigators and the Sponsor Clinical Director. However, abnormalities of liver blood tests that do not meet the criteria noted above are not ECIs for this trial.

Table 6–6: Guidance on Assessment and Further Dosing Following Occurrence of Hepatic Events of Clinical Interest

Assessment procedure to be applied

- Notification of the sponsor within 24 hours via SAE report if applicable (see also Section 8.3). Refer to Section 8.3.6 for AEs of special safety interest that must be reported as SAEs
- Consider a consultation with a hepatologist.
- Consider a work-up for hepatitis if there is no underlying hepatitis, including hepatitis A, B, C, D, E, Epstein-Barr virus (EBV), cytomegalovirus (CMV).
- Assess for ingestion of drugs/supplements with hepatotoxic potential.
- Assess for alcohol ingestion.
- · Assess for potential bacterial infection, biliary obstruction, or occult gastrointestinal bleeding
- Repeat ALT, AST, t-bilirubin, direct bilirubin, ALP, GGT, INR, and CBC (complete blood count) with differential.
- Other laboratories or imaging studies as clinically indicated.
- Consider liver biopsy if indicated by hepatologist.

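### In protocol Table 6-5, a bleed from esophageal varices meets two rows whose pembrolizumab guidance is inconsistent, and nothing in the documents says which row governs

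*Protocol*

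**What the plan says.** Three rows at the end of Table 6-5 (protocol Section 6.6.2) matter here.

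- **Portal-hypertension bleeding row.** The event is "Gastrointestinal bleeding suggestive of portal hypertension", with esophageal and gastric varices given as examples. Regorafenib is to be discontinued. The pembrolizumab entry is "Hold and assess + decide on potential restart according to guidance given in" Table 6-6.
- **Recurrence row.** The event is "Recurrence of a severe or life-threatening event, or of any of the laboratory abnormalities listed above". Both drugs are to be discontinued.
- **Last row.** This is a composite. It covers being off treatment for more than 3 weeks for certain causes, "or if they have esophageal bleeding, or become CP C at any point". The entry for both drugs is "Discontinue and assess according to guidance given in" Table 6-6.

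On the status of the table, its general instructions state: "The recommendations regarding dose adjustments and treatment interruptions can be used as support for the clinical decision". The introduction to Section 6.6 says the same of Tables 6-3 to 6-8. Section 7.1.1.3 says that participants may, not must, be withdrawn from pembrolizumab for an event that Section 6.6 treats as requiring permanent discontinuation.

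SAP Section 5.4.1.2 plans separate summaries of treatment-emergent adverse events (TEAEs) leading to discontinuation and of those leading to dose interruption. Each is given for any study drug, regorafenib, pembrolizumab and both.

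**The concern.** The two bleeding rows overlap. One leaves pembrolizumab restart open; the other does not. A site facing an esophageal variceal bleed can follow the table and reach either result.

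The pembrolizumab entry carries weight because regorafenib stops in both rows. Section 4.1.1.2 allows one drug to continue after the other has been permanently discontinued for toxicity. So the pembrolizumab entry decides whether the participant can stay on any study treatment.

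The event is foreseeable. Exclusion criterion 15 in Section 5.2 keeps out participants with large at-risk varices only if these are not being treated, and Appendix 10 is devoted to varices. The risk has also been reduced on purpose: entry requires Child-Pugh A, and bleeding diathesis and Grade 3 or higher bleeding within 28 days are excluded. Cirrhosis is not itself an entry requirement, because histological or cytological confirmation is an alternative to the non-invasive diagnosis.

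**Working it through.** There is no figure in the plan to reproduce. The check compares the rows and then looks for any rule that separates them.

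**Step 1: the rows side by side, for one esophageal variceal bleed**

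| | Portal-hypertension bleeding row | Last row |
|---|---|---|
| Is the event covered? | Yes, named as an example | Yes, esophageal bleeding without limit on source, severity or recurrence |
| Regorafenib | Discontinue | Discontinue |
| Pembrolizumab | Hold, assess, decide on restart | Discontinue |

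The overlap is narrow. A gastric variceal bleed falls only in the first of these rows. An esophageal bleed unrelated to portal hypertension falls only in the last.

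**Step 2: is there a reading that reconciles them?**

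- *Hold and discontinue as synonyms.* No. The pembrolizumab column uses them as different actions: hold for ALT/AST above 5 x ULN, discontinue for AST and/or ALT above 20 x ULN.
- *First bleed in one row, recurrent bleed in the other.* No. Recurrence has its own row between the two.
- *The 3-week condition limits the last row.* No. It attaches to time off treatment for infection, obstruction or drug/alcohol toxicity. Esophageal bleeding follows as a new alternative.
- *Footnotes.* Footnote a concerns the lowest regorafenib dose and neutropenia, and footnote b hepatic encephalopathy. Neither mentions bleeding.
- *Table 6-6.* Bleeding appears only as a work-up item: "Assess for potential bacterial infection, biliary obstruction, or occult gastrointestinal bleeding". The pembrolizumab restart conditions are set out for hepatitis B flare, hepatitis C recurrence or flare, immune-related hepatitis and other causes. They turn largely on recovery of ALT or other laboratory values, and none names a bleed.

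**Step 3: which bleeds are already directed elsewhere?**

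- Recurrent severe or life-threatening events go to the recurrence row, which discontinues both drugs.
- For Grade 4 non-hematologic events, Table 6-3 advises discontinuing pembrolizumab, after consulting the sponsor and if the toxicity is at least possibly related to pembrolizumab.

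That leaves mainly first, non-Grade-4 esophageal variceal bleeds.

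**Step 4: what moves in the reported results?**

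Take one participant with one such bleed. Assume that the site follows one row exactly, that pembrolizumab is restarted if held, and that an entry under both drugs means the event led to that action for each drug.

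| SAP 5.4.1.2 summary | Hold, then restart | Discontinue |
|---|---|---|
| Discontinuation, any drug | Yes | Yes |
| Discontinuation, regorafenib | Yes | Yes |
| Discontinuation, pembrolizumab | No | Yes |
| Discontinuation, both | No | Yes |
| Interruption, any drug | Yes | No |
| Interruption, regorafenib | No | No |
| Interruption, pembrolizumab | Yes | No |
| Interruption, both | No | No |

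Four of the eight entries depend on the row chosen. The secondary endpoint in protocol Section 3 counts participants with a dose modification, pooling interruption, reduction and discontinuation. This participant counts once in either column, since regorafenib is discontinued in both.

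**The case against.** The strongest reply has three parts.

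1. **The table is guidance.** It supports a decision that rests with the investigator, and Section 7.1.1.3 is permissive for pembrolizumab where Section 7.1.1.2 is mandatory for regorafenib. Some variation between sites would remain even if the rows agreed. This stands as a limit on the consequence. It does not remove the conflict: guidance that points two ways gives an investigator no support for this event, and Section 7.1.1.3 itself refers back to Section 6.6 to identify events requiring permanent discontinuation.

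2. **The rows are not opposites.** A hold with a decision on restart includes not restarting, and both rows send the site to Table 6-6. That is fair. A reader might infer that one row requires restart and the other forbids it, but the text does not go that far. The rows differ in the discretion they leave, and that difference is real.

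3. **The reach is small.** A reader might infer that every esophageal variceal bleed is affected, or that a secondary endpoint depends on the row chosen. The documents support neither. Some recurrent and Grade 4 bleeds already have a direction elsewhere, and the pooled dose-modification count is the same under both rows. No hypothesis test uses the TEAE tables that can shift. The SAP version history also records that recruitment stopped prematurely, which limits how many participants could be exposed.

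**Conclusion.** The inconsistency is real and should be corrected. For a bleed from esophageal varices, Table 6-5 gives two pembrolizumab instructions that differ on whether restart is open, with no rule of precedence.

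Its scope is one drug, one type of bleed, and mainly first events below Grade 4, within a table of recommendations. The possible effects are different management of the same event across sites, and movement of that event between the descriptive pembrolizumab interruption and discontinuation tables. The primary endpoint analysis does not use these rows, and the pooled dose-modification count is unchanged.

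The number of events cannot be estimated, because the documents give no expected frequency of variceal bleeding. The conclusion rests on reading esophageal bleeding in the last row as including a variceal source, which is its ordinary meaning and which nothing in the table excludes.

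**What to change.** The sponsor should reconcile the two rows of Table 6-5 so that a single pembrolizumab instruction applies to bleeding from esophageal varices, or should state which row takes precedence. If restart remains possible under the reconciled text, the reference to Table 6-6 should lead to a condition that covers bleeding, since at present it does not. Which instruction is right is a clinical matter for the sponsor, and nothing is proposed here.

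The cost is wording in one table, plus a line in Table 6-6 if that route is kept. No sample size, endpoint or analysis changes.

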6.6.2.1 Hepatic Events of Clinical Interest

The following events and laboratory abnormalities, if not associated with disease progression under study per investigator's judgement, are considered as hepatic events of clinical interest (HECI) and must be reported as SAEs (within 24 hours of the investigator's awareness):

- ALT:
 - ALT \geq 5 × ULN if baseline ALT <2 x ULN
 - ALT >3 × baseline level if baseline ALT \geq 2 x ULN
 - Any ALT >500U/L
- Any t-bilirubin >3.0 mg/dL
- Regardless of laboratory values, hepatic decompensation diagnosed clinically, including:
 - New onset of clinically detectable ascites requiring intervention for >3 days
 - Hepatic encephalopathy

Note: These criteria are based upon available regulatory guidance documents. The purpose of the criteria is to specify a threshold of abnormal hepatic tests that may require an additional evaluation for an underlying etiology. The trial site guidance for assessment and follow up of these criteria can be made available. It may also be appropriate to conduct an additional evaluation for an underlying etiology in the setting of abnormalities of liver blood tests including ALT and bilirubin that do not meet the criteria noted above. In these cases, the decision to proceed with additional evaluation will be made through consultation between the study investigators and the Sponsor Clinical Director. However, abnormalities of liver blood tests that do not meet the criteria noted above are not ECIs for this trial.

Table 6–6: Guidance on Assessment and Further Dosing Following Occurrence of Hepatic Events of Clinical Interest

Assessment procedure to be applied

- Notification of the sponsor within 24 hours via SAE report if applicable (see also Section 8.3). Refer to Section 8.3.6 for AEs of special safety interest that must be reported as SAEs
- Consider a consultation with a hepatologist.
- Consider a work-up for hepatitis if there is no underlying hepatitis, including hepatitis A, B, C, D, E, Epstein-Barr virus (EBV), cytomegalovirus (CMV).
- Assess for ingestion of drugs/supplements with hepatotoxic potential.
- Assess for alcohol ingestion.
- · Assess for potential bacterial infection, biliary obstruction, or occult gastrointestinal bleeding
- Repeat ALT, AST, t-bilirubin, direct bilirubin, ALP, GGT, INR, and CBC (complete blood count) with differential.
- Other laboratories or imaging studies as clinically indicated.
- Consider liver biopsy if indicated by hepatologist.
- Infection needs to be ruled out with cultures of blood, urine, and ascites (if possible), as well as chest X-ray and abdominal imaging if relevant. If an infection is found, antibiotics should be started
- If t-bilirubin is elevated above baseline, magnetic resonance cholangio-pancreatography or ultrasound with Doppler should be obtained to rule out vascular compromise, biliary obstruction, and/or tumor progression.
- If biliary obstruction is present, consultation with a gastroenterologist and/or an interventional radiologist should be obtained to see if the obstruction may be relieved.
- A careful review of drugs, including herbal and alternative medications, should be obtained, and alcohol use should be ruled out.
- Hepatitis C-infected participants (including participants who previously achieved sustained

Page 68 of 141

Table 6–6: Guidance on Assessment and Further Dosing Following Occurrence of Hepatic Events of Clinical Interest

virological response [SVR] for 12 consecutive weeks after the cessation of antiviral treatment [SVR 12]): Measure HCV RNA viral load.

 Hepatitis B-infected participants: HBV DNA, HBsAg, HBeAg, anti-HBc (total and IgM), anti-HBe, and anti-HBs; participants should be questioned about compliance with the use of antiviral agents

Further information concerning Hepatitis B Flare

Hepatitis B flares are characterized by rapid elevations of ALT and AST to >5 × ULN and/or >3 × baseline. ALT elevation to ≥10 × ULN is common. In the absence of hepatic decompensation, ALT/AST elevations are typically isolated (i.e., limited/no elevations of bilirubin/ALP). Participants who are compliant with antiviral therapy should have continued suppression of HBV DNA at the time of flare; thus, detection of HBV DNA should prompt questioning of participants for compliance. Laboratory abnormalities secondary to flare are typically observed for 3-5 weeks.

Among participants with HBV, a flare should be considered if this pattern is observed and there is no evidence of an alternative etiology. Guidelines for participants with a diagnosis of HBV flare are as follows:

- Care should be instituted in consultation with a hepatologist.
- For participants who have detectable HBV DNA, re-institute antiviral therapy.
- If the participant is clinically stable, pembrolizumab dosing may be interrupted for up to 12 weeks. Participants should undergo weekly laboratory tests including: AST, ALT, ALP, Tbil, Dbil, INR, HBsAg, HBV DNA (if detected at the onset of the flare). Obtain anti-HBe, anti-HBs, and HBV DNA levels (if not detected at the onset of the flare) every 2-3 weeks.
- Restart pembrolizumab intervention only if ALT returns to normal or Grade 1 (if normal at baseline), or to baseline grade (if Grade 2 at baseline) within 12 weeks, and the participant is clinically stable, otherwise the participant should be permanently discontinued.

Further information concerning Hepatitis C Recurrence or Flare

Participants who achieved SVR 12 and participants with ongoing HCV infection are eligible for enrollment. In rare circumstances, HCV participants who achieve SVR 12 may relapse at later time points. Relapse is characterized by detection of HCV RNA, often accompanied by ALT elevations to >5 × ULN. In the absence of hepatic decompensation, ALT/AST elevations are typically isolated (i.e., limited/no elevations of bilirubin/ALP).

Among participants with uncontrolled hepatitis C, virologic flares are possible. Hepatitis C flares are characterized by rapid elevations of ALT and AST to >5 × ULN and/or >3 × baseline along with a rise in HCV RNA. ALT elevation to ≥10 × ULN and a 1 log elevation in HCV RNA level are common. In the absence of hepatic decompensation, ALT/AST elevations are typically isolated (i.e., limited/no elevations of bilirubin/ALP). Laboratory abnormalities secondary to flare or recurrence are typically observed for 3-5 weeks.

Guidelines for participants with recurrent HCV infection or an HCV flare are described below:

- Interrupt pembrolizumab intervention for up to 12 weeks
- Restart pembrolizumab intervention only if ALT returns to normal or G1 (if normal at baseline), or to baseline grade (if G2 at baseline) within 12 weeks, and the participant is clinically stable, otherwise, the participant should be permanently discontinued

Recurrent HCV infection (relapse of HCV infection for participants successfully treated or with new HCV infection):

If the participant entered the study with an HCV RNA test of "Target not Detected" and has confirmed detectable HCV RNA (2 specimens, 1 week apart), then the participant has experienced a late HCV relapse or a recurrent infection.

- Question the participant about use of injection or inhalation drugs
- At the time of first detection of HCV RNA, send a specimen for HCV genotyping or serotyping (if genotyping is not available) (local laboratory)
- Measure AST, ALT, ALP, Tbil, Dbil, and INR weekly
- Measure HCV RNA levels every 2 weeks
- Therapy with HCV antiviral treatments should be strongly considered.

HCV Flare (hepatitis C exacerbation in participants with HCV RNA positive):

 At the time of first detection of HCV RNA, send a specimen for HCV genotyping or serotyping (if genotyping is not available) (local laboratory)

Page 69 of 141

Table 6–6: Guidance on Assessment and Further Dosing Following Occurrence of Hepatic Events of Clinical Interest

- Measure AST, ALT, ALP, Tbil, Dbil, INR weekly
- Measure HCV RNA levels every 2 weeks
- Therapy with HCV antiviral treatments should be strongly considered

Further information concerning Immune-related hepatitis

Description: Immune-related hepatitis due to study treatment should be suspected if any of the following is seen:

- ALT baseline values are less than 2 × ULN, and AST or ALT laboratory values increase to ≥5 × ULN
- Among participants with baseline ALT ≥2 × ULN, levels increase to >3× the baseline level
- ALT >500 U/L regardless of baseline level
- Total bilirubin >3.0 mg/dL regardless of baseline level

Immune-related hepatitis is a diagnosis made after excluding other possible etiologies for the change. Viral flare (if applicable), biliary or vascular obstruction, infection, medications, and alcohol use must be ruled out (see below).

Management:

- Interrupt pembrolizumab intervention for up to 12 weeks
- Start IV corticosteroid (60 mg/day of prednisone or equivalent) followed by oral corticosteroid
 - Monitor with biweekly laboratory tests including AST, ALT, Tbil, Dbil, ALP, and INR
 - Restart pembrolizumab intervention only if:
 - Abnormal laboratory values resolve to Grade ≤1 or baseline (if abnormal at baseline)
 - Taper steroid over 28 days
 - Steroid treatment is tapered to prednisone <10 mg/day or equivalent
 - Permanently Discontinue pembrolizumab intervention if:
 - Laboratory abnormalities do not resolve within 3 weeks
 - Steroids cannot be lowered to ≤10 mg/day (or prednisone equivalent) within 12 weeks
 - o Evidence of decompensation to CP C status

Further information concerning other causes:

- Rule out infection with blood, urine and ascites culture antibiotics should be started if infection is found
- If total bilirubin is elevated, imaging should be obtained to rule out vascular compromise, biliary obstruction, and/or tumor progression by imaging. If biliary obstruction is present, consultation with a gastroenterologist and/or an interventional radiologist should be obtained to see if the obstruction may be relieved.
- · Ruled out alcohol use and hepatotoxic drugs including herbal and alternative medications
- Interrupt pembrolizumab intervention for up to 12 weeks
- Restart pembrolizumab only if laboratory values have returned to Grade 1 or baseline (if normal or Grade 1 at start) or to baseline grade within 3 weeks

AE = adverse event; ALP = alkaline phosphatase; ALT = alanine aminotransferase; anti-HBc = Hepatitis B core antibody; anti-HBe = hepatitis B e-antigen; anti-HBs = hepatitis B surface antibody; AST = aspartate aminotransferase; CP = Child-Pugh (score); Dbil = direct bilirubin; dL = deciliter; DNA = deoxyribonucleic acid; G1/2/3/4 = Grade 1/2/3/4; GGT = gamma-glutamyl transferase; HBeAg = Hepatitis B e-antigen; HBsAg = hepatitis B surface antigen; HBV = hepatitis B virus; HCV = hepatitis C virus; IV = intravenous; IgM = Immunoglobulin M; INR = international normalized ratio; mg = milligram; RNA = ribonucleic acid; SAE = serious adverse event; SVR = sustained viral response; Tbil = total bilirubin; ULN = upper limit of normal

6.6.3 Dose Modification and Toxicity Management for Immune-related AEs Associated with Pembrolizumab

AEs associated with pembrolizumab exposure may represent an immunologic etiology. These irAEs may occur shortly after the first dose or several months after the last dose of pembrolizumab treatment and may affect more than one body system simultaneously. The irAEs may be fatal and may occur after discontinuation of pembrolizumab. Therefore, early recognition and initiation of treatment is critical to reduce complications. Based on existing clinical trial data, most irAEs were reversible and could be managed with interruptions of pembrolizumab, administration of corticosteroids and/or other supportive care. For suspected irAEs, ensure adequate evaluation to confirm etiology or exclude other causes. Additional procedures or tests such as bronchoscopy, endoscopy, skin biopsy may be included as part of the evaluation. Based on the severity of irAEs, withhold or permanently discontinue pembrolizumab and administer corticosteroids.

Table 6-7: Dose Modification Guidance, Other Immune-related Adverse Events

Event	Regorafenib	Pembrolizumab	
Specific guidance for IMMUNE-	RELATED ADVERSE EVENTS		
General instructions concerning	g pembrolizumab:		
	1. Severe and life-threatening irAEs should be treated with IV corticosteroids followed by oral steroids. Other immunosuppressive treatment should		
begin if the irAEs are not	controlled by corticosteroids.		
Pembrolizumab must be j	permanently discontinued if the irAE does not resolve or the cort	ticosteroid dose is not ≤10 mg/day within 12 weeks of the	
last pembrolizumab treatr	ment.		
The corticosteroid taper s	hould begin when the irAE is ≤ Grade 1 and continue at least 4	weeks.	
4. If pembrolizumab has bee	en withheld, pembrolizumab may resume after the irAE decrease	ed to ≤ Grade 1 after corticosteroid taper.	
Pneumonitis	 G2 or higher: Interrupt until ≤ G1 	G2: Withhold	
 Monitor participants for 	 Restart at same dose level for G2 and decrease by 	Recurrent G2, G3, or G4: Permanently discontinue	
signs and symptoms of	1 dose level for G3/4 ^a	Administer corticosteroids (initial dose of 1-2 mg/kg	
pneumonitis		prednisone or equivalent) followed by taper: add	
 Evaluate participants with 		prophylactic antibiotics for opportunistic infections	
suspected pneumonitis with			
radiographic imaging and			
initiate corticosteroid			
treatment			

Table 6–7: Dose Modification Guidance, Other Immune-related Adverse Events

Event	Regorafenib	Pembrolizumab
Specific guidance for IMMUNE	-RELATED ADVERSE EVENTS	
New onset Type 1 Diabetes Mellitus (T1DM) or G3 or G4 hyperglycemia associated with evidence of β-cell failure • Monitor participants for hyperglycemia or other signs and symptoms of diabetes	• Interrupt until ≤ G1. Restart at same dose level.	 Withhold^b Initiate insulin replacement therapy for participants with T1DM Administer anti-hyperglycemic in participants with hyperglycemia
 Hypophysitis Monitor for signs and symptoms of hypophysitis (including hypopituitarism and adrenal insufficiency) 	• Interrupt until ≤ G1. Restart at same dose level.	 G2: Withhold G3/4: Withhold or discontinue (at the investigator's discretion)^b Administer corticosteroids and initiate hormonal replacements as clinically indicated
Monitor for signs and symptoms of thyroid disorders	 G2: No modifications G3/4: Interrupt until ≤ G2. Restart at same dose level. 	 G2: Continue G3/4: Withhold or discontinue (at the investigator's discretion)^b Treat with non-selective beta-blockers (e.g. propranolol) or thionamides as appropriate
 Hypothyroidism Monitor for signs and symptoms of thyroid disorders 	 No modification Initiate thyroid replacement hormones (e.g. levothyroxine or liothyronine) per standard of care 	 Continue Initiate thyroid replacement hormones (e.g. levothyroxine or liothyronine) per standard of care
Monitor changes of renal function; grading according to increased creatinine or acute kidney injury	 G2: Continue G3/4: Interrupt until ≤ G2. Restart at same dose level. 	 G2: Withhold G3/4: Permanently discontinue Administer corticosteroids (prednisone 1-2 mg/kg or equivalent) followed by taper
Neurological toxicities	 G2 or higher: Interrupt until ≤ G1 Restart at same dose level for G2 and decrease by 1 dose level for G3/4a 	 G2: Withhold G3/4: Permanently discontinue Based on severity of AE administer corticosteroids

Table 6–7: Dose Modification Guidance, Other Immune-related Adverse Events

Event	Regorafenib	Pembrolizumab
Specific guidance for IMMUNE	RELATED ADVERSE EVENTS	
Myocarditis Ensure adequate evaluation to confirm etiology and/or exclude other causes	 G2 or higher: Interrupt until ≤ G1 Restart at same dose level for G2 and decrease by 1 dose level for G3/4^a 	 Grade 1: Withhold Grade 2/3/4: Permanently discontinue Based on severity of AE administer corticosteroids
Exfoliative dermatologic conditions	 Suspected Steven-Johnson Syndrome (SJS), toxic epidermal necrolysis (TEN), or drug rash with eosinophilia and systemic symptoms (DRESS): Withhold Confirmed SJS, TEN, or DRESS: Permanently discontinue Based on severity of AE administer corticosteroids Ensure adequate evaluation to confirm etiology or exclude other causes 	 Suspected SJS, TEN, or DRESS: Withhold Confirmed SJS, TEN, or DRESS: Permanently discontinue Based on severity of AE administer corticosteroids
All other immune-related AEs (e.g. immune-mediated arthritis, pancreatitis, uveitis, etc.) • Ensure adequate evaluation to confirm etiology or exclude other causes	 G2 or higher: Interrupt until ≤ G1 Restart at same dose level for G2 and decrease by 1 dose level for G3/4^a 	 Persistent G2: Withhold G3: Withhold or discontinue based on the event^c Recurrent G3 or G4: Permanently discontinue Based on severity of AE administer corticosteroids

AE = adverse event; DRESS = drug rash with eosinophilia and systemic symptoms; G1/2/3/4 = Grade 1/2/3/4; irAEs = immune-related adverse event; IV = intravenous; QD = every day; SJS = Steven-Johnson Syndrome; T1DM = type 1 diabetes mellitus; TEN = toxic epidermal necrolysis

